#### 1 PROTOCOL SUMMARY

# 1.1 Synopsis

**Protocol Title:** A 4-part Phase 1/2 study to evaluate the safety, tolerability, pharmacokinetics, and pharmacodynamics of M254 in healthy volunteers and in patients with immune thrombocytopenic purpura. This study was opened in Europe in 2018 (EudraCT: 2018-003534-32) as a 4-part study. Part A enrolled 25 healthy volunteers at a single site in the Netherlands and has been completed. This study will open in the United States (US) as a 3-part study with Parts B, C, and D; no subjects in the USA will be enrolled in Part A.

**Short Title:** Safety and tolerability of M254 in healthy volunteers and immune thrombocytopenic purpura (ITP) patients

#### Rationale:

Intravenous immunoglobulin has been used for the treatment of a variety of acute and chronic autoimmune and systemic inflammatory diseases for decades [1, 3, 15, 13]. At the current maximal dosing regimens, only partial and transient responses are obtained in many clinical instances [3, 15]. In addition, the long infusion times (4 to 6 hours) associated with the high volume of IVIg treatment consume significant resources at infusion centers [6] and negatively affect patient-reported outcomes, such as convenience and quality of life [9]. M254 is expected to be many fold more potent compared to commercially available IVIg based on preclinical pharmacological experiments. This may lead to reduced infusion time for patients compared to commercially available IVIg. Hypersialylation may increase IVIg-related anti-inflammatory and immune-modulating activities.

Intravenous immunoglobulin is an approved therapy for the treatment of ITP with prompt increases in platelet counts as early as a day after treatment with peak platelet response occurring within 2 to 7 days. This known treatment effect with easily measurable pharmacodynamics (PD) endpoint of increasing platelet count makes ITP patients a suitable population for investigation of M254. The present 4-part (each part will be initiated sequentially), first in-human study will be conducted first in healthy subjects and subsequently in ITP patients to evaluate the safety, tolerability, pharmacokinetics (PK), and PD platelet response of M254 administered as single followed by multiple intravenous (IV) doses.

Compound: M254 Protocol: MOM-M254-001

Protocol Date and Version:8 Global 28 April 2020

The study will be executed in 4 distinct parts. Part A will assess safety, tolerability, and PK of M254 after administration of a single ascending dose in healthy volunteers (no subjects in the USA will be enrolled in Part A). Part B will assess safety, tolerability, and PK of M254 after administration of a single ascending dose of M254 followed by 1000 mg/kg IVIg administration in ITP patients. Part C will be a 2-arm, crossover design comparing the PD platelet response of M254 with IVIg in patients with ITP. Part C will have 2 cohorts with doses to be determined following analysis of data from Parts A and B. Part D will be a repeat dose study of M254 for the evaluation of safety, tolerability, PK, and PD platelet response in patients with ITP.

# **Objectives and Endpoints**

### Part A (Netherlands only)

OBJECTIVES	ENDPOINTS
OBJECTIVES	ENDPOINTS
Primary	
To assess the safety and tolerability of a single ascending dose of intravenous administration of M254 in healthy	• Incidence and severity of adverse events (AEs) following administration of M254 at single dose levels
volunteers	
 
Clinically significant changes in clinical safety labs, vital signs, and electrocardiograms (ECGs) with M254 administration
 

Secondary	
To characterize the pharmacokinetics (PK) of a single intravenous administration of M254 at different doses in healthy volunteers	Measurements of PK parameters of M254 following the administration of a single intravenous dose
Exploratory	
To characterize the pharmacodynamics (PD) of a single intravenous administration of M254 at different doses in healthy volunteers	Exploratory biomarkers relating M254 exposure to potential efficacy in autoimmune diseases and the M254 mechanism of action may be analyzed

Compound: M254 Protocol: MOM-M254-001

Protocol Date and Version:8 Global 28 April 2020

# Part B (USA sites included)

OBJECTIVES	ENDPOINTS								
Primary									
To assess the safety and tolerability of a single intravenous administration of M254 in immune thrombocytopenia (ITP) patients compared to 1000 mg/kg intravenous immunoglobulin (IVIg)	
 
Incidence and severity of adverse events         (AEs) following administration of M254         at single dose levels and 1000 mg/kg         IVIg
 
Clinically significant changes in clinical         safety labs, vital signs, and         electrocardiograms (ECGs) following         M254 administration and 1000 mg/kg         IVIg
 
								
Secondary									
To characterize the pharmacokinetics (PK) of a single intravenous administration of M254 at different doses in ITP patients	Measurements of PK parameters of M254 following the administration of a single intravenous dose								
Exploratory									
To characterize the pharmacodynamics (PD) of a single intravenous administration of M254 at different doses in ITP patients compared to IVIg	
 
Platelet response after M254         administration compared to IVIg
 
Exploratory biomarkers relating M254         exposure to potential efficacy in         autoimmune diseases and the M254         mechanism of action may be analyzed
 
								

Compound: M254 Protocol: MOM-M254-001

Protocol Date and Version:8 Global 28 April 2020

# Part C (USA sites included)

OBJECTIVES	ENDPOINTS							
Primary								
To assess the safety of a single intravenous administration of M254 compared to 1000 mg/kg of intravenous immunoglobulin (IVIg)     To characterize the pharmacodynamics (PD) of single intravenous administration of M254 compared to 1000 mg/kg IVIg	
 
Incidence and severity of adverse events         (AEs) of M254 and 1000 mg/kg IVIg
 
Clinically significant changes in clinical         safety labs, vital signs, and         electrocardiograms (ECGs) following         M254 administration and 1000 mg/kg         IVIg
 
Platelet response after M254         administration compared to IVIg
 
							
Secondary	•							
To characterize the pharmacokinetics (PK) of a single intravenous administration of M254 at different doses	Measurements of PK parameters of M254 following the administration of a single intravenous dose							
Exploratory								
To characterize the PD of single intravenous administration of M254 compared to 1000 mg/kg IVIg	Exploratory biomarkers relating M254 exposure to potential efficacy in autoimmune diseases and the M254 mechanism of action may be analyzed							

# Part D (USA sites included)

OBJECTIVES	ENDPOINTS
Primary	
To assess the safety and tolerability of repeated intravenous administration of M254 in immune thrombocytopenia (ITP) patients	
 
Incidence and severity of adverse events         (AEs) with repeated administration of         M254
 
Clinically significant changes in clinical         safety labs, vital signs, and         electrocardiograms (ECGs) with M254         administration
 

Secondary	

 
To characterize the pharmacokinetics (PK) of repeated intravenous doses of M254 in ITP patients
 
	Measurements of PK parameters of M254 following the administration of a repeated intravenous doses

Compound: M254 Protocol: MOM-M254-001

Protocol Date and Version:8 Global 28 April 2020

## **Hypothesis:**

[figure not shown]
No formal hypothesis testing will be used.

# **Overall Design:**

This is a Phase 1/2, study investigating single and repeated administration of M254 in a 4-part study. The overall design of each part (A, B, C, and D) is summarized below (Figure 1-1). A Scientific Review Committee (SRC) will review safety data as described in each of the parts below. Adverse events (AEs) will be graded using the Common Terminology Criteria for Adverse Events (CTCAE), version 5.0. For all healthy volunteers and patients with ITP, a 28-day duration of safety monitoring following dosing of either M254 or IVIg has been selected based on nonclinical comparability of PK between M254 and IVIg, and clinical observations with IVIg where platelets return to ≤15% above baseline within 28 days.

For Parts B, C, and D of the study, during the follow-up period, participants may have laboratory assessments, vital signs, electrocardiogram (ECG), and PK samples assessed at home or another location mutually agreed with the site, but can be seen by the study staff if complications arise or for participant comfort.

Figure 1-1. Overall Schematic of 4-part Study Design Versus Timing

#### Part A (Netherlands only)

Part A is a single-ascending-dose, randomized, double-blinded sponsor unblind, safety, tolerability, and PK assessment of M254 or placebo in 6 cohorts of healthy volunteers. Planned doses include 3, 10, 30, 60, 120, and 250 mg/kg. In Cohort 1, 5 subjects will be enrolled with 3:2 (active:placebo) randomization. In all other cohorts, subjects will be randomized 3:1 (active:placebo) with total of 4 subjects in each cohort. There will be approximately 25 subjects in Part A. Up to 2 additional cohorts may be added based on

Compound: M254 Protocol: MOM-M254-001

Protocol Date and Version:8 Global 28 April 2020

findings in prior cohorts. Additional dosing cohorts may be added on the recommendation of the SRC.

Following screening to confirm eligibility to participate, subjects will be randomized to receive M254 or placebo. Please refer to Section 4.3.1 and Figure 1-2 for dosing details.

At the first dose level (3 mg/kg), a sentinel group of 2 subjects (1 M254, 1 placebo) will be dosed and closely monitored for 48 hours before dosing the remainder of the cohort (2 M254, 1 placebo). The subjects in this sentinel group will be closely observed by the Investigator for any safety signals for the first 48 hours following drug administration. The general tolerability of the study drug will be monitored during this time and the ECG recordings and vital signs data will be reviewed. In addition, any reported AEs will be considered by the Investigator. If the safety and tolerability results of the first 48 hours following dosing for the initial subjects are acceptable to the Investigator, the other subjects in Cohort 1 of Part A may be dosed. There will be no additional sentinel groups in the study beyond this cohort (Cohort 1 Part A).

Safety assessments will be conducted out to Day 28 post M254 dosing. The SRC will review all available safety data after each cohort has completed at least 10 days of assessments after the single dose of M254. Dose escalation will only proceed after the recommendation of the SRC.

The SRC will review all safety data for all subjects in Part A out to Day 28.

[figure not shown]
Cohorts in Part B may start before the completion of Part A; however, prior to initiation of any cohort in Part B, either the same or a higher dose level will have been given in Part A and have a positive recommendation by the SRC, with the exception of doses greater than 250 mg/kg.

Dose escalation and continuation to the next study part may only occur when the SRC has given a positive recommendation and the Ethical Committee has given a statement of no objection, as per local requirement (where required).

Compound: M254 Protocol: MOM-M254-001

Protocol Date and Version:8 Global 28 April 2020

Figure 1-2. Part A Study Schema

Note: Arrows represent dose escalation; Safety will be assessed prior to dose escalation.

- a Up to 2 additional cohorts may be added based on findings in prior cohorts.
- In Cohort 1, dosing will be initially limited to a sentinel group (1 active, 1 placebo) that will be monitored for at least 48 hours before the remainder of the cohort is dosed.

### Part B (USA sites included)

Initiation of any cohort in Part B will only proceed on the recommendation of the SRC after safety data from Part A Cohort 4 at the 60-mg/kg dose level has been reviewed and confirmed by SRC.

Part B is a single-ascending-dose, fixed-sequence, open-label part to assess safety, tolerability, PK, and PD of M254 followed by 1000 mg/kg IVIg in 4 cohorts of 2 ITP patients per cohort. Planned doses include 60, 120, 250, and 500 mg/kg. Up to 2 additional cohorts may be added based on findings in prior cohorts to better understand the safety of M254 and/or to better understand the efficacy to assist with dose selection for Part C. The maximum dose for Part B will not exceed 500 mg/kg (the no-observed-adverse-event-level [NOAEL] of 1000 mg/kg was determined in the toxicology study in cynomolgus monkeys). Additional patients may be added to dosing cohorts, including prior dose level cohorts, on the recommendation of the SRC.

Compound: M254 Protocol: MOM-M254-001

Protocol Date and Version:8 Global 28 April 2020

Following screening to confirm eligibility to participate, patients will be dosed with M254. Please refer to Section 4.3.1 and Figure 1-3 for dosing details. There will be a 14-day safety monitoring period between enrollment of the first and second patients in the 500 mg/kg cohort.

[figure not shown]
Safety and platelet assessments will be conducted initially out to Day 28 post M254 administration. Patients will receive a fixed dose of IVIg at 1000 mg/kg on Day 29 if the patients' platelet count returns to  $\leq 15\%$  above baseline level. Patients whose platelets have not returned to  $\leq 15\%$  above baseline dosing level by Day 28 will have platelet determinations weekly until platelets return to  $\leq 15\%$  above baseline, up to 56 days postdose. If these conditions are not met by Day 57, IVIg will be administered, as long as the patients' platelets have returned to  $\leq 15\%$  above baseline and are  $\geq 50 \times 10^9/L$ , the patient will complete Follow-Up assessments and be discharged from Part B. After dosing with IVIg, safety and the other assessments listed in the Schedule of Activities will be conducted for 28 days following IVIg administration.

The SRC will review all safety data for all patients in Part B up to at least 28 days following M254 administration for the last patient. Initiation of Part C will only proceed on the recommendation of the SRC. Dose escalation and continuation to the next study part may only occur when the SRC has given a positive recommendation and the Ethical Committee has given a statement of no objection, as per local requirement (where required).

Compound: M254 Protocol: MOM-M254-001

Protocol Date and Version:8 Global 28 April 2020

Figure 1-3. Part B Study Schema

Note: Arrows represent dose escalation; Safety will be assessed prior to dose escalation.

IVIg = Intravenous immunoglobulin; NOAEL = no-observed-adverse-event-level.

- a Up to 2 additional cohorts may be added based on findings in prior cohorts. Additional patients may be added to cohorts, including prior dose level cohorts. Maximum dose will not exceed 500 mg/kg (a NOAEL of 1000 mg/kg determined in the toxicology study in cynomolgus monkeys).
- b All patients will receive a dose of IVIg (1000 mg/kg) at approximately Day 29.

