## 4.1.3 Part C (including sites within the USA)

Part C consists of 2 randomized, unblinded crossover cohorts to assess safety and PD of a single dose of M254 compared to a single dose of IVIg in ITP patients. The dose of M254 for each of these 2 cohorts will be determined after analysis of the data from Part A and Part B. Each cohort consists of 10 patients with 2 arms in each cohort consisting of 5 patients in each arm, for an overall total of 20 patients in Part C.

Following screening to confirm eligibility to participate, in crossover Cohort 1 or Cohort 2, 5 patients in each cohort will be randomized to M254 by IV administration and 5 patients will be randomized to 1000 mg/kg IVIg. Please refer to Section 4.3.1 and Figure 1-4 for dosing details.

Safety and platelet assessments will be conducted initially out to Day 28 post M254 or IVIg administration. Patients will receive their dose of either M254 or IVIg, depending on their assigned arm within the cohort, on Day 29 if the patients' platelet count returns to  $\leq 15\%$  above baseline level. Patients whose platelets have not returned to  $\leq 15\%$  above baseline dosing level by Day 28 will have platelet determinations weekly until platelets return to  $\leq 15\%$  above baseline up to 56 days post the first M254 or IVIg administration. Patients who do not meet this criteria will receive the second administration of M254 or IVIg, as long as the platelets have returned to  $\leq 50 \times 10^9/L$ . If the platelets have not returned to  $\leq 15\%$  above baseline and are  $\geq 50 \times 10^9/L$ , the patient will complete Follow-Up assessments on or around Day 57 post first infusion and be discharged from Part C; and the patient may be replaced. After patients are crossed over to the second administration of M254 or IVIg, they are followed for an additional 28 days with safety and platelet assessments or until platelet counts return to  $\leq 15\%$  above their baseline level following similar rules to the first dose in Part C.

The SRC will review all safety data from both crossover cohorts in Part C; however, the initiation of Part D will proceed after the SRC reviews all safety data from Cohort 1 and the recommendation is to proceed with Part D. Dose escalation and continuation to the next study part may only occur when the SRC has given a positive recommendation and the Ethical Committee has given a statement of no objection, as per local requirement (where required).

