#### 9 STATISTICAL CONSIDERATIONS

#### 9.1 Sample Size Determination

The sample size has been chosen to provide adequate numbers of subjects and patients to characterize the safety, tolerability, PK, and PD of M254 and the study has not been formally powered.

No formal sample size calculation was performed for this study (Parts A, B, and D).

Part C is an exploratory study designed to obtain preliminary information on the safety and efficacy of M254 for the treatment of ITP.

Assuming ratio of M254 to IVIg in maximum change from baseline of platelet counts as **EG** 

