Initiation of any cohort in Part B will only proceed on the recommendation of the SRC after safety data from Part A Cohort 4 at the 60 mg/kg dose level has been reviewed and confirmed by SRC. Part B is a single ascending dose, fixed-sequence, open-label part to assess safety, tolerability, PK, and PD of M254 followed by 1000 mg/kg IVIg in approximately 4 cohorts of 2 ITP patients per cohort. Planned doses include 60 mg/kg, 120 mg/kg, 250 mg/kg and 500 mg/kg. Up to 2 additional cohorts may be added based on findings in prior cohorts to better understand the safety of M254 and/or to better understand the efficacy to assist with dose selection for Part C. The maximum dose for Part B will not exceed 500 mg/kg (the NOAEL of 1000 mg/kg determined in the toxicology study in Cynomolgus monkeys). Additional patients to dosing cohorts may be added on the recommendation of the SRC. Patients will receive a fixed dose of IVIg at 1000 mg/kg on Day 29 if the patients' platelet count returns to \leq 15% above baseline level. Patients whose platelets have not returned to \leq 15% above baseline dosing level by Day 28 will have platelet determinations weekly until platelets return to \leq 15% above baseline, up to 56 days post-dose. If these conditions are not met by Day 57. IV lg will be administered, as long as the patients' platelets have returned to $< 50 \times 10^{9}$ /L. If the platelets have not returned to \leq 15% above baseline and are > 50 × 10⁹/L, the patient will complete Follow-Up assessments and be discharged from Part B. After dosing with IVIg, safety and the other assessments listed in the Schedule of Activities will be conducted for 28 days following IV lg administration.

Figure 3: Part B Schema

Note: Arrows represent dose escalation; Safety will be assessed prior to dose escalation.

IVIg = Intravenous immunoglobulin; NOAEL = no-observed-adverse-event-level.

- ^a Up to 2 additional cohorts may be added based on findings in prior cohorts. Additional patients may be added to cohorts, including prior dose level cohorts. Maximum dose will not exceed 500 mg/kg (a NOAEL of 1000 mg/kg determined in the toxicology study in cynomolgus monkeys).
- ^b All patients will receive a dose of IVIg (1000 mg/kg) at approximately Day 29.

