The SRC will review all safety data for all patients in Part B up to at least 28 days following M254 administration for the last patient. Initiation to Part C will only proceed on the recommendation of the SRC. Part C consists of 2 randomized, unblinded crossover cohorts, to assess safety and PD of a single dose of M254 compared to a single dose of IVIg in ITP patients. The dose of M254 for each of these 2 cohorts will be determined after analysis of the data from Part A and Part B. Each cohort consists of 10 patients with 2 arms in each cohort consisting of 5 patients in each arm, for an overall total of 20 patients in Part C. Following screening to confirm eligibility to participate, in crossover Cohort 1 or Cohort 2, 5 patients in each cohort will be randomized to M254 by IV administration and 5 patients will be randomized to 1000 mg/kg IVIg. Patients will receive 1 dose of either M254 or IVIg, depending on their assigned arm within the cohort on Day 29 if the patients' platelet count returns to ≤15% above baseline level. Patients whose platelets have not returned to ≤15% above baseline dosing level by Day 28 will have platelet determinations weekly until platelets return to ≤15% above baseline up to 56 days post the first M254 or IVIg administration. Patients who do not meet this criteria will receive the second administration of M254 or IVIg, as long as the platelets have returned to $< 50 \times 10^{9}$ /L. If the platelets have not returned to $\leq 15\%$ above baseline and are $> 50 \times 10^{9}$ /L. 10⁹/L, the patient will complete Follow-Up assessments on or around Day 57 post first infusion and be discharged from Part C; and the patient may be replaced. After patients are crossed over to M254 or IVlg, they are followed for an additional 28 days with safety and platelet assessments or until platelet counts return to ≤15% above their baseline level following similar rules to the first dose in Part C.

Figure 4: Part C Schema

IVIg = Intravenous immunoglobulin; TBD = to be determined.

- ^a Patients will be followed for 28 days or until their platelet counts have returned to ≤15% above baseline levels and then crossed to the second period. Patients will again be dosed and followed for an additional 28 days with safety and platelet assessments.

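### The Day 57 fallback rule for the second infusion handles a platelet count of exactly 50 × 10⁹/L in three different ways, and its Part B synopsis version cannot be carried out as printed

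*Protocol*

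**What the plan says.** In Part B the ordinary route to the second infusion is a return of platelets to no more than 15% above baseline: "Patients will receive a fixed dose of IVIg at 1000 mg/kg on Day 29 if the patients' platelet count returns to" that level. If this has not happened by Day 28, counts continue weekly up to 56 days after dosing. Part C uses the same route for its crossover.

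A fallback rule then covers patients who still have not returned. For Part B, the synopsis and section 4.1.2 both begin "If these conditions are not met by Day 57, IVIg will be administered", with a platelet condition attached. For Part C, section 4.1.3 says "Patients who do not meet this criteria will receive the second administration of M254 or IVIg, as long as" platelets have come down to a limit. Patients above that limit complete follow-up and leave, and in Part C they may be replaced.

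SAP section 6.0 restates both rules. For Part B, a patient not dosed under the fallback leaves: "the patient will complete Follow-Up assessments and be discharged from Part B". For Part C it says "Patients who do not meet this criteria will receive the second administration of M254 or IVIg, as long as the platelets have returned to" a limit. SAP section 7.1, on changes from the protocol, lists only an addition to the definition of a therapeutic platelet count.

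**The concern.** The rule should send each patient in the fallback to exactly one outcome: a second infusion or discharge. The documents state it five times (Part B synopsis, section 4.1.2, Part C synopsis, section 4.1.3, and SAP section 6.0 for both parts) with inequality signs that do not match. At the boundary value the result depends on which statement is read. One further statement, in the Part B synopsis, contradicts itself.

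The rule decides who receives the second product, who is discharged and, in Part C, who may be replaced. It therefore affects which patients supply both periods to the Part C comparison of M254 with IVIg. That comparison is the primary platelet analysis and has 5 patients per sequence in each cohort of 10. Sites also need an instruction they can follow without choosing between sections.

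**Working it through.** No sample-size or power figure is involved; the protocol says "the study has not been formally powered". The check is one of logic.

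**The statements side by side** (counts in 10⁹/L; all apply to patients still more than 15% above baseline)

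| Place | Second infusion if | Discharge if | At exactly 50 |
|---|---|---|---|
| Protocol 4.1.2 (Part B) | ≤50 | ≥50 | both |
| Protocol 4.1.3 (Part C) | ≤50 | ≥50 | both |
| Part C synopsis | <50 | ≥50 | discharge |
| SAP 6.0 (Parts B and C) | <50 | >50 | neither |
| Part B synopsis, as printed | ≤15% above baseline and ≥50 | same condition, same sentence | neither |

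**Inputs.** Baseline B is ≥15 and <50 (ITP inclusion criterion 4). Whole-number baselines are assumed, 15 to 49, which gives 49 − 15 + 1 = 35 values. Whole-number counts c run from 15 to 200, an assumed range wide enough to show the pattern. The fallback applies when c > 1.15 × B.

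**Which baselines can meet the boundary problem.** A count of 50 is in the fallback only if 50 > 1.15 × B, that is B < 50/1.15 = 43.5. At B = 43, 1.15 × 43 = 49.45, so 50 is in the fallback. At B = 44, 1.15 × 44 = 50.6, so 50 already satisfies the ordinary 15% route. The problem can therefore arise for baselines 15 to 43, which is 43 − 15 + 1 = 29 of the 35.

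**Outcome of each rule** over all 5,728 baseline/count pairs in the fallback:

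| Rule | Dose only | Discharge only | Both | Neither |
|---|---|---|---|---|
| 4.1.2 and 4.1.3 | 467 | 5,232 | 29 | 0 |
| Part C synopsis | 467 | 5,261 | 0 | 0 |
| SAP 6.0 | 467 | 5,232 | 0 | 29 |
| Part B synopsis, as printed | 0 | 0 | 0 | 5,728 |

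Each row sums to 5,728 (for example 467 + 5,232 + 29). The 29 pairs that move between columns are all at c = 50. At every other count the first three rules agree. The pair counts test the logic and are not probabilities.

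**The Part B synopsis sentence.** Its trigger is that the 15% return has not occurred (c > 1.15 × B), yet its dosing condition requires that return (c ≤ 1.15 × B). No value satisfies both. Even without the trigger, the condition together with ≥50 needs B of at least 43.5, so only baselines 44 to 49 could meet it. The sentence also attaches ≥50 to the IVIg clause and then discharges the patient. Compared with section 4.1.2, the two match through "If these conditions are not met by Day 57, IVIg will be administered, as long as the patients' platelets have returned to" and match again from "above baseline and are $\geq 50 \times 10^9/L$ , the patient will complete Follow-Up assessments and be discharged from Part B". What the synopsis lacks is the text between two occurrences of the same phrase about platelets having returned.

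**The case against.** Several points on the other side have force.

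- **Lost text.** The gap in the Part B synopsis, between two identical phrases, is what a skipped line would produce. The clause is intact in 4.1.2 and the SAP. This stands: the sentence is not established as a sponsor error until the original is checked.
- **A reversed rule.** A reader might infer that the synopsis reverses the rule for every Part B patient still above the return criterion at Day 57. The documents do not support that. Such a patient fails the printed condition, so the sentence selects nobody; it is unusable, not reversed.
- **Universal conflict at 50.** A reader might also infer that every patient with a count of 50 is caught. Those with baselines of 44 to 49 are not, because the ordinary 15% route already applies to them.
- **Unreliable signs.** The boundary conflict also depends on inequality signs as read. The SAP gives its baseline subgroup as ≤30 versus >30 in section 9.4.2 but ≤30 versus ≥30 in 17.2.2.1. This partly stands. However, the pattern is the same across Parts B and C within 4.1.2/4.1.3 and within the SAP, and the SAP discharge sentences show ≤15% and >50 together. Misreading is less likely, but not excluded.
- **The SAP does not direct dosing.** Section 3.0 says it supersedes the protocol's statistical considerations, so its design summary should not decide who is infused. It also cites a protocol dated 24 April 2020, whereas the one supplied is dated 28 April, which might explain a difference. Neither point removes the overlap inside 4.1.2 and 4.1.3, or the mismatch between 4.1.3 and the Part C synopsis.
- **Limited analytic effect.** Part B platelet response is exploratory. In Part C the Full Analysis Set needs only one post-infusion assessment, so a discharged patient still contributes the first period. This stands and limits the size of the problem.

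**Conclusion.** The inconsistency is real but narrow. As printed, a fallback patient with a count of exactly 50 × 10⁹/L meets both outcomes under 4.1.2 and 4.1.3, discharge alone under the Part C synopsis, and neither under SAP 6.0. The SAP does not declare the difference. It needs a count of exactly 50 at the decision and a baseline of about 43 or below. The documents give no data on how often that happens, and nothing in them shows that any patient was misallocated. The practical effect is expected to be small, though in Part C one patient gaining or losing a second period is noticeable with 5 per sequence in a cohort.

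Separately, the Part B synopsis sentence cannot be carried out as printed, and whether that is a drafting error is open. The verdict assumes whole-number counts, the stated entry range for baseline, and inequality signs that match the originals. It takes no position on which threshold is right.

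**What to change.** First check the Part B synopsis sentence and the inequality signs against the original documents. Then reconcile the Part B and Part C synopses, protocol sections 4.1.2 and 4.1.3, and SAP section 6.0 to one statement of the Day 57 rule. Its dosing and discharge conditions should not overlap and should together cover every count. The choice of threshold, and of the side on which 50 falls, belongs to the sponsor. Any intended difference between SAP and protocol should be listed in SAP section 7.1.

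The statistical output appended to the SAP is dated 30 November 2021, so conduct appears to be complete. The study report should therefore state which rule was applied and whether any patient reached the decision with a count of exactly 50. The cost is wording and a short check of the fallback cases; no design or analysis changes.
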